5.7.2 Analysis of Primary Pharmacodynamic Endpoint

5.7.2.1 Endpoint, Treatment Effect and Estimand Definition

To assess the primary objective, the primary estimand has the following key attributes:

- Population of interest: healthy adult male participants as defined by the listed inclusion/exclusion criteria in Section 5.1 and 5.2 of the protocol.
- Variable/endpoint of interest: CMAP total amplitude at Week 28, measured as percentage relative to baseline (%), calculated as [value at Week 28 (mean of the three measurements/baseline value (means of the six measurements)]*100.

- ICEs are the following:
 - a) Study discontinuation
 - b1) PDs with potential impact on relevant CMAP total amplitude assessments (i.e. participant received the wrong study intervention and CMAP at Week 28 performed out of a specified time window ($> +/- 2$ weeks))
 - b2) PDs with no expected impact on relevant CMAP assessments (e.g. other time window violations, PDs related to covid-19)
- Treatment regimen: Dysport, Botox or Xeomin will be administered as described in Section 6 of the protocol and potential intake of permitted concomitant medications (for a list see Section 6.8 of the protocol).
- Population-level summary of the treatment effect of interest: the difference in average percentage relative to baseline in each study intervention group in CMAP total amplitude at the respective timepoint.

For ICEs (a) and (b1) a hypothetical strategy will be used, the treatment difference which would have been measured if the ICE would not have happened is of interest and will be assessed taking into account the long term pharmacodynamic effect of the investigated compounds. This implies that assessments after the occurrence of a major protocol deviation interfering with CMAP total amplitude will be ignored for the primary analysis. No imputation of missing CMAP will be done (MMRM analysis, please refer to [section 5.7.1.2](#)). For ICEs (b2), a treatment policy will be used.

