6.8 Concomitant Therapy

Any prior medications/nondrug therapies used by the participant within 30 days prior to the Screening visit (and not continued during the study) or concomitant medications/nondrug therapies given during the study will be indicated on the eCRF. Dose and generic name or trade name will be indicated.

The investigator will be advised not to use any dermal topics (including anaesthetic topics) on the participant prior to the injection of study intervention on Day 1. In addition, the following concomitant medications are not permitted during this study:

- Any form of BoNT (other than the specific study intervention) for administration into any site of the body.
- Any experimental new drug or device.
- Medications that affect neuromuscular transmission, such as curare-like non-depolarising agents, lincosamides, polymyxins, anticholinesterases and aminoglycoside antibiotics, within the past 30 days of Baseline and during the study.
- Medications that affect bleeding disorders (antiplatelet agents and/or anticoagulants given for treatment or prevention of cardiovascular /cerebrovascular diseases).
- Concomitant medications for other purposes are allowed at the investigator's discretion. It is recommended that the dosage for these medications is kept constant throughout the study. Where medically appropriate, all concomitant medications being taken by a participant at entry into the study should continue at the same dose.

Concomitant use of anticholinergic drugs (which may potentiate systemic anticholinergic effects) is permitted if the dosage has been stable for the 6 weeks prior to study intervention and is expected to remain at this stable dose throughout the study.

Concomitant use of any vaccine against COVID-19 is permitted from 7 days after injection of study intervention. COVID-19 vaccination dates should not be delayed to enable study participation. Participants who are unable to adhere to the COVID-19 vaccination guidance outlined in this protocol should not be included in the study (also see Section [5.2](#)).

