9.4.2 Analysis of Primary Endpoint(s)

9.4.2.1 Primary Estimand

The primary estimand has the following key attributes:

- Population of interest: healthy adult male participants as defined by the listed inclusion/exclusion criteria in Section 5.
- Variable/endpoint of interest: CMAP total amplitude at Week 28, measured as relative change from Baseline (%).
 - a) Key Intercurrent event (ICE): study discontinuation
 - b) Major protocol deviation interfering with CMAP total amplitude.
- Treatment regimen: Dysport, Botox or Xeomin will be administered as described in Section 6 and potential intake of permitted concomitant medications (for a list see Section 6.8).
- Population-level summary of the treatment effect of interest: the difference in average relative change from baseline in each study intervention group in CMAP total amplitude at the respective timepoint.

For ICEs (a) and (b) a hypothetical strategy will be used, the treatment difference which would have been measured if the intercurrent event would not have happened is of interest and will be assessed taking into account the long term pharmacodynamic effect of the investigated compounds. This implies that assessments after the occurrence of a major protocol deviation interfering with CMAP total amplitude will be ignored for the primary analysis.

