5.3 Protocol Deviations

An exhaustive list of major Protocol Deviations (PDs) that may occur during the course of the study is defined in the PDs plan. Major PDs will be determined before unblinding of the study, finalised during the blind data review and documented in a PDs list.

Following PDs summary and listing will be provided on the randomised set:

- Number and percentage of participants with major PDs by deviation category
- A listing of major PDs.
- A listing of major PDs potentially having an impact on primary efficacy analysis:
 - o Participant received the wrong study intervention (Mis randomisation)
 - o CMAP at Week 28 or Week 40 performed out of a specified time window (> +/- 2 weeks)

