5.7.1.2 Handling of Dropouts and missing data

Diligent attempts will be made to limit the amount of missing data and to follow-up all randomised participants to collect the primary and secondary pharmacodynamic endpoints for the statistical analysis.

The Mixed Model for Repeated Measures (MMRM) is implicitly handling missing data as Missing At Random (MAR) without explicit imputation. This missingness assumption appears meaningful given the long term pharmacodynamic effect of the investigated compounds: the effect of the drug will persist after discontinuation and is not expected, given baseline profile of the participant and assessments until the timepoint of discontinuation, to depend on whether the participant remains observable in the study or drops out.

In case of occurrence of a major PDs with the potential to interfere with CMAP total amplitude (see [Section 5.3](#)), CMAP data collected after the PDs will be ignored, and will be handled by the model as MAR. This implements a 'per protocol' analysis assessing the treatment difference occurring in case participants adhere to the protocol by using a hypothetical handling strategy for this ICE.

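### SAP 5.7.3.1 gives two conflicting rules for scoring Week 28 recovery after a mistimed visit, and the rule of ignoring later CMAP does not fit a timing deviation

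*SAP*

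**What the plan says.** **Protocol.** Section 9.4.2.1 names a second intercurrent event without a list: "Major protocol deviation interfering with CMAP total amplitude". It is handled by a hypothetical strategy, so later assessments are ignored. Section 6.8 prohibits, among others, "Any form of BoNT (other than the specific study intervention) for administration into any site of the body" and "Medications that affect neuromuscular transmission, such as curare-like non-depolarising agents".

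**SAP, scope.** Section 5.7.2.1 splits the event. Class b1 is "PDs with potential impact on relevant CMAP total amplitude assessments (i.e. participant received the wrong study intervention and CMAP at Week 28" more than 2 weeks off schedule, introduced by *i.e.* Class b2 covers deviations with no expected impact, gives its members as examples, and uses treatment policy. Section 5.7.3.1 repeats this for the key secondary endpoints, with the timing item tied to the visit concerned. Section 5.3 states that "An exhaustive list of major Protocol Deviations (PDs) that may occur during the course of the study is defined in the PDs plan". Under "A listing of major PDs potentially having an impact on primary efficacy analysis" it gives the same two items, plus Week 40 timing. Section 2.6 declares clarifications only.

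**SAP, data rule.** Section 5.7.1.2: "CMAP data collected after the PDs will be ignored, and will be handled by the model as MAR". Section 5.7.2.1: "This implies that assessments after the occurrence of a major protocol deviation interfering with CMAP total amplitude will be ignored for the primary analysis". Section 5.7.3.1 says the same for the key secondary endpoints.

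**SAP, recovery rule.** The same bullet of 5.7.3.1 then scores a participant with an intercurrent event as not recovered if the next available CMAP is below 85% of baseline. Otherwise, or if no CMAP is available after the event, recovery is imputed.

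**The concern.** The next available CMAP after an event is itself an assessment after the event. If later assessments are ignored, none is available and the default is recovery. If the next one is used, later assessments have not been ignored. The bullet does not say which sentence prevails.

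The data rule also suits a deviation with a lasting effect, not a visit on the wrong date. For a mistimed Week 28 the doubtful value is the Week 28 value itself, and Weeks 32-40 may be on schedule.

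What is at stake is mainly Week 28 recovery. It is third in the fixed sequence, it gates Week 40 recovery, and it is tested with 15 per arm, where a single status can matter. Choosing between the readings after unblinding would be open to challenge as data-driven.

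**Working it through.** **Planning inputs (SAP 2.3).** Difference 18, SD 15, 15 per arm, two-sided 5%. SE of a difference = 15 × √(2/15) = 5.48. Noncentrality = 18/5.48 = 3.29 on 28 df, giving power 88.7% (stated: at least 88%). Simulating rejection of both hypotheses gives 81.4% (stated: at least 81%). The inputs reproduce; they serve here only to scale the consequences.

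**1. Recovery, the two rules side by side.** Take a participant who has not recovered before Week 28, whose Week 28 visit is more than 2 weeks off, and who is below 85% at Week 32.

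| Sentence in 5.7.3.1 | Week 32 value | Week 28 status |
|---|---|---|
| Later assessments ignored | not available | Recovery |
| Next available CMAP decides | below 85% | No recovery |

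For Week 40 there is normally no later CMAP, so both sentences give recovery. After discontinuation at most an early-withdrawal CMAP exists (SAP 6.2 moves it to the next empty visit). The conflict therefore matters mainly for b1 deviations at Week 28.

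**2. What one status can do (one-sided Fisher, 2.5%, 15 v 15).**
- Dysport 4/15 v comparator 11/15: p = 0.0134. Dysport 5/15 v 11/15: p = 0.0328.
- Of the 51 tables significant in Dysport's favour with at least one Dysport participant not recovered, 11 lose significance when one more Dysport participant is counted as recovered.

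**3. How often it decides a comparison.** Assume one such Dysport participant. Let X ~ Bin(14, pD) be recoveries among the other Dysport participants and Y ~ Bin(15, pC) those in the comparator arm. The quantity is Pr(reject | X, Y) − Pr(reject | X+1, Y), by exact enumeration. The recovery rates are assumptions; the documents give none.

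| pD | pC 0.6 | pC 0.7 | pC 0.8 | pC 0.9 |
|---|---|---|---|---|
| 0.2 | 17.5% | 16.2% | 10.1% | 3.1% |
| 0.3 | 11.7% | 15.7% | 15.0% | 7.9% |
| 0.4 | 6.2% | 11.4% | 15.1% | 12.4% |
| 0.5 | 2.6% | 6.2% | 11.3% | 14.3% |

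The range is 2.6% to 17.5%. A comparator participant scored in two ways would move the result in the opposite direction.

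**4. The data rule applied to a mistimed Week 28.** Read literally, it keeps the off-window value and drops Weeks 32-40.
- Off-window value kept: with an assumed recovery of 1-3 points per week and 2-4 weeks off, the arm mean moves by (1 × 2)/15 = 0.13 to (3 × 4)/15 = 0.80 points, against an SE of 5.48.
- Later visits dropped: generalised least squares with known covariance, 11 visits, one participant of 15 affected. Removing Weeks 28-40, compared with removing Week 28 only, changes the SE as follows.

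| Assumed correlation | Week 28 SE | Week 40 SE |
|---|---|---|
| AR(1), 0.5 to 0.9 per 4 weeks | +0.15 to +0.30% | +1.01 to +1.76% |
| Compound symmetry, 0.5 to 0.9 | +0.01 to +0.03% | +0.20 to +1.00% |

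**5. Scope.** The protocol's event covers any interfering major deviation. Use of a prohibited agent that interferes with CMAP meets that description. It is not one of the two b1 items, and it cannot be b2, which is for deviations with no expected impact. The SAP therefore assigns it no strategy.

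**The case against.** **The specific recovery sentence can override the general one.** That is a sensible reading, and probably the intended one. The bullet does not say so, however, and two programmers could implement it differently.

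**The literal reading of the data rule is uncharitable.** The hypothetical strategy implies that the off-window value should go, and 5.7.3.1 ties timing to the visit concerned. This is fair as to intent, but the written rule refers only to what comes after the deviation.

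**Supplementary analyses exist.** SAP 5.7.2.4 and 5.7.3.4 report treatment-policy results with all collected data. This is real mitigation, but it does not settle which rule governs the main analysis.

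**A closed list is legitimate.** Protocol 9.4 leaves further detail to the SAP, and deviations are finalised at blind data review. This largely stands. A reader might infer that the SAP has improperly rewritten the primary estimand. The documents do not support that: listing items is permitted, and the protocol deviations plan, which is not available, may cover part of the gap. What remains is an unassigned class and a Section 2.6 that does not mention the narrowing.

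**COVID-19.** A reader might infer that naming COVID-19 deviations under b2 exempts a badly mistimed Week 28 visit that had that cause. The b2 heading, and its reference to other time window violations, point the other way, so no criticism is made on that score.

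**Conclusion.** The concern holds, and its weight lies in the recovery rule. SAP 5.7.3.1 contains two instructions that can score the same participant in opposite ways on an alpha-controlled endpoint. The size is conditional: a Week 28 visit must be more than 2 weeks off, in a participant not yet recovered and still below 85% at Week 32, and both hypotheses must already have been rejected for the primary endpoint and for Week 40 amplitude. Given all that, one Dysport status decides a single comparison in about 3-18% of trials over the assumed rates. The documents do not say how often such deviations occur.

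A reader might infer that the primary analysis is compromised. It is not: under the stated assumptions mistiming moves an arm mean by 0.1-0.8 points and adds at most 0.3% to the Week 28 SE. The Week 40 SE rises by 0.2-1.8%. The prohibited-agent gap is a smaller drafting matter. Overall this lies between a minor point and one that should be fixed. It is worth correcting because the correction is cheap and is only clean before unblinding.

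**What to change.** SAP wording, before unblinding:

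- **Timing deviations.** In 5.7.1.2, 5.7.2.1 and 5.7.3.1, state that for a Week 28 or Week 40 CMAP outside the 2-week limit only that value is set to missing, and all other visits are kept.
- **Recovery.** In 5.7.3.1, state that for timing deviations recovery at the affected visit is decided from the next available in-window CMAP, as an explicit exception to the sentence on ignoring later assessments.
- **Scope.** Align b1 and 5.3 with the protocol's event by adding prohibited agents judged at the blind data review to interfere with CMAP. Exclude only the CMAP values judged affected; deleting every later visit would repeat the over-deletion seen with mistimed visits.
- **Record.** Enter these in 2.6 and align the protocol deviations plan.

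The cost is a few sentences and a little more work at blind data review. No new data are needed, and neither the model nor the sample size changes.

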5.7.2.2 Primary Analysis

The primary endpoint, CMAP total amplitude at Week 28, measured as percentage relative to baseline (%), will be analysed using a mixed-effects model for MMRM. The model will include fixed effects of treatment, time (corresponding to study visits when CMAP is measured, i.e. Day 7, Weeks 4, 8, 12, 16, 20, 24, 28, 32, 36 and 40), treatment-by-time interaction and baseline CMAP amplitude, as well as an unstructured covariance matrix to model the covariance structure of the repeated measures.

Using the mixed-effects model described above, the Dysport versus Botox and Dysport versus Xeomin comparisons in the primary endpoint at Week 28 of the study will be investigated using the according partial tests (i.e. mixed model Wald tests). Results of the primary analysis will contain an estimate of the treatment difference between Dysport and comparators Botox and Xeomin in CMAP total amplitude at Week 28, as well as Standard Error (SE), 95% CI, and p-value.

The SAS code to be used is presented in [appendix A4](#).

Analysis will be based on the primary estimand described in [section 5.7.2.1](#).

5.7.2.3 Sensitivity Analysis

No sensitivity analyses will be performed.

5.7.2.4 Supplementary Analysis

In case of occurrence of major PDs with the potential to interfere with CMAP total amplitude ([see section 5.3](#)), a supplementary analysis using the same MMRM model used for the primary analysis will be conducted using a treatment policy strategy to handle this ICE. All collected CMAP data will be taken into account in this supplementary analysis, even when occurring after PDs.

5.7.2.5 Subgroup Analysis

No subgroup analyses will be performed.

5.7.3 Analysis of Key Secondary Pharmacodynamic Endpoints

5.7.3.1 Endpoint, Treatment Effect and Estimand Definition

To assess the secondary objectives, the key secondary endpoints and estimands have the following key attributes:

- Population of interest: healthy adult male participants as defined by the listed inclusion/exclusion criteria in Section 5.1 and 5.2 of the protocol.
- Secondary endpoint of interest:
 - CMAP total amplitude at Week 40, measured as percentage relative to baseline (%), calculated as [value at Week 40 (mean of the three measurements)/baseline value (means of the six measurements)]*100
 - Incidence at Week 28 of recovery of CMAP total amplitude
 - Incidence of recovery of CMAP total amplitude at Week 40

The recovery is considered to be reached for all the visits occurring after the time to recovery, i.e. the first visit for which CMAP total amplitude return to at least 85% of the baseline value.

- ICEs are the following:
 - b) Study discontinuation
 - b1) PDs with potential impact on relevant CMAP total amplitude assessments (i.e. participant received the wrong study intervention and time window violation at the corresponding time point ($> +/- 2$ weeks)),
 - b2) PDs with no expected impact on relevant CMAP assessments (e.g. other time window violations, PDs related to covid-19)
- Treatment regimen: Dysport, Botox or Xeomin will be administered as described in Section 6 of the protocol and potential intake of permitted concomitant medications (for a list see Section 6.8 of the protocol).
- For ICEs (a) and (b1) a hypothetical strategy will be used, the treatment difference which would have been measured if the ICE would not have happened is of interest and will be assessed taking into account the long term pharmacodynamic effect of the investigated compounds. This implies that assessments after the occurrence of a major protocol deviation interfering with CMAP total amplitude will be ignored for the analysis. For CMAP total amplitude at Week 40, no imputation will be done (MMRM analysis). For the incidence of recovery, it will be considered as "No recovery" if the next available percentage CMAP relative to baseline (%) is inferior to 85% and will be imputed to the worst scenario "Recovery" if not or in case of no available CMAP after this ICE.

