4.3 Justification for Dose

Dysport 40 U has already been shown to be well tolerated when injected into the EDB [[Pons 2019](#)], as well as demonstrating an absence of local diffusion to the adjacent muscles. This dose level was also associated to a remaining CMAP inhibition 6 months post-injection.

When applying a ratio of 2.5 (Dysport) for 1 (Botox/Xeomin), which is based on the maximum recommended total doses in the USPI from the FDA from adult upper limb spasticity and glabellar lines indications, a dose of 16 U is selected for Botox and Xeomin. Doses of 16 U Botox or Xeomin were also shown to be safe when injected into the EDB [[Wohlfarth 2007](#)].

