7.2 Participant Discontinuation/Withdrawal from the Study

- A participant may withdraw from the study at any time at his own request or may be withdrawn at any time at the discretion of the investigator for safety, behavioural or compliance reasons.
- At the time of discontinuing from the study, if possible, an early withdrawal visit should be conducted, as shown in the SoA. See SoA for data to be collected at the time of study discontinuation and follow-up and for any further evaluations that need to be completed.
- The reason for discontinuation will be recorded in the eCRF.
- If the participant withdraws consent for disclosure of future information, the sponsor may retain and continue to use any data collected before such withdrawal of consent.
- If the participant withdraws consent, it should be explained in detail in the medical records by the investigator as to whether the withdrawal is only from further receipt of study intervention or also from study procedures and/or posttreatment study follow-up. This information must be entered in the eCRF.
- If a participant withdraws from the study, he may request destruction of any samples taken and not tested, and the investigator must document this in the site study records.

A participant may discontinue participation in the study at any time for any reason (e.g. lack of efficacy, withdrawal of consent, adverse event (AE)). The investigator and/or sponsor can withdraw a participant from the study at any time for any reason (e.g. protocol violation or deviation noncompliance with the protocol conditions or AEs). All cases of discontinuation will be discussed between the investigator and the sponsor.

If a participant decides to withdraw from the study after administration of IMP, or should the investigator decide to withdraw the participant, all efforts will be made to complete and report the observations up to the time of withdrawal as thoroughly as possible. A complete final evaluation at the time of the participant's withdrawal should be made and an explanation given of why the participant is withdrawing or being withdrawn from the study.

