6 DATA HANDLING

6.1 Visit window

Time window (+/- 2 weeks) is used to calculate the protocol deviations defined as ICE for the analysis.

No other time windows are needed for analyses.

6.2 Unscheduled Visits, Retest, Withdrawal Visit,

All listings will include retests and unscheduled visits, while for the description by visit in the tables, only the scheduled visits according to the protocol will be described.

Unscheduled visit and retest measurements will be used to provide a measurement for a baseline data or endpoint value (e.g. worst value), if appropriate according to their definition.

If a value requires a retest (for vital signs) the closest non-missing reliable value to the scheduled visit will be used in the summary tables.

An assessment will be considered reliable if it is performed without any technical problem and if the result is within the range of likely values.

Participants who have withdrawn early from the study have their last assessment entered as visit 90 in the eCRF. By convention, for these participants, the visit number will be reassigned to the next empty visit number (i.e. if a participant has Visit 1, 2, 3 and 90 entered in the database, the visit number 90 will be reassigned to visit number 4) for summary tables.

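### The recovery imputation in SAP 5.7.3.1 does not require the next available CMAP to fall at or after Week 28 or Week 40, so a withdrawn man's score is either unsupported or depends on how the rule is read

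*SAP*

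**What the plan says.** SAP 5.7.3.1 applies a hypothetical strategy to study discontinuation and to deviations with potential impact on CMAP (wrong study intervention, or a target visit more than 2 weeks off schedule). For the recovery endpoints it then imputes. The score is *No recovery* "if the next available percentage CMAP relative to baseline (%) is inferior to 85" per cent. It is *Recovery*, labelled the worst scenario, "if not or in case of no available CMAP after this ICE".

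Four other statements bear on this:

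- The same bullet says that "assessments after the occurrence of a major protocol deviation interfering with CMAP total amplitude will be ignored for the analysis".
- The endpoint definition in the same section carries recovery forward: "The recovery is considered to be reached for all the visits occurring after the time to recovery".
- Protocol 7.2: "At the time of discontinuing from the study, if possible, an early withdrawal visit should be conducted, as shown in the SoA". The Schedule of Activities includes a CMAP recording in the EoS/EW column.
- SAP 6.2: "Participants who have withdrawn early from the study have their last assessment entered as visit 90 in the eCRF". That assessment is moved to the next empty visit number, but this is stated only for summary tables.

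Recovery at Week 28 and at Week 40 are key secondary endpoints. Each is tested by a one-sided Fisher exact test at 2.5%, inside the sequential Hochberg scheme (SAP 5.7.1.3 and 5.7.3.2.2).

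**The concern.** A CMAP below 85% of baseline is evidence against recovery at a given visit only if it is taken at or after that visit. Before recovery, most injected muscles should be below 85%; Protocol 4.3 says of Dysport 40 U: "This dose level was also associated to a remaining CMAP inhibition 6 months post-injection". A low value early in the effect therefore says little about Week 28 or Week 40. It also does not answer the hypothetical question the SAP sets, which is what would have been measured had the event not happened.

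After discontinuation, the only CMAP the plan schedules is the one at the withdrawal visit. If it counts as following the event, it decides the score however early it was taken. If it does not, or if the man skips the visit, he is scored the opposite way. What is at stake is the score of each early withdrawal on two alpha-controlled endpoints, in arms of 15 where one man can move a p-value across 0.025.

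**Working it through.** **1. Inputs.** From the documents: 15 per arm, 85% threshold, one-sided Fisher at 2.5%, withdrawals not replaced. The plan's stated power of at least 88% (difference 18, SD 15, two-sided 5% t-test) reproduces at 88.7% from the noncentral t with 28 df, but it concerns the primary endpoint. No recovery rate or withdrawal rate is given, so every rate below is an assumption.

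**2. Tracing the rule.**

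| Case | CMAP counted as after the event | Not counted, or ignored |
|---|---|---|
| Leaves at Week 6, withdrawal CMAP 20% of baseline | *No recovery* at Weeks 28 and 40, from a value 28 − 6 = 22 and 40 − 6 = 34 weeks too early | *Recovery* at both |
| Leaves between Weeks 28 and 40, not yet recovered, withdrawal CMAP below 85% | *No recovery* at Week 40 only | *Recovery* at Week 40 |
| Wrong study intervention on Day 1, Day 7 CMAP below 85% | *No recovery* at both | *Recovery* at both, since post-deviation data are ignored |
| Target visit more than 2 weeks off schedule | Next CMAP is normally a later visit, so the rule is sensible | *Recovery* |

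The third row assumes the man stays in the pharmacodynamic set. That set requires the appropriate dose, and the SAP does not say whether a wrong product fails this condition.

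**3. Effect of *No recovery* scores when there is no true difference.** Let d men in an arm be fixed as not recovered and the other 15 − d recover with probability π. Enumerate both binomials exactly and sum the probability of tables with one-sided Fisher p ≤ 0.025. With d in the Dysport arm only, the bias in the risk difference is −dπ/15. At π = 0.8:

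| d | Bias, Dysport only | Rejection, Dysport only | Comparator only | d in each arm |
|---|---|---|---|---|
| 0 | 0 | 0.8% | 0.8% | 0.8% |
| 1 | −5.3 points | 1.7% | 0.09% | 0.24% |
| 2 | −10.7 points | 3.3% | 0.01% | 0.07% |
| 3 | −16.0 points | 5.8% | <0.01% | 0.04% |

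At π = 0.7 the Dysport-only rates for d = 1, 2, 3 are 1.5%, 2.4% and 4.0%, so 2.5% is passed only at d = 3.

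**4. Sensitivity of one result.**

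- Suppose the true table is 6/15 Dysport v 12/15 comparator: p = 0.030, not significant at 0.025.
- One Dysport man who would have recovered is scored *No recovery*: 5/15 v 12/15, p = 0.013.
- One such comparator man instead: 6/15 v 11/15, p = 0.070.
- One in each arm: 5/15 v 11/15, p = 0.033.

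**5. Dilution under a true difference.** Assume normal CMAP percentages with SD 15, comparator mean 95 and Dysport mean 95 − 18 = 77. Recovery is then Φ((95 − 85)/15) = 0.748 for the comparator and Φ((77 − 85)/15) = 0.297 for Dysport, a difference of −0.451. If a share q withdraws in each arm and all are scored *No recovery*, the difference becomes (1 − q) × (−0.451): −0.406 at 10% and −0.360 at 20% (from unrounded rates). Fisher power falls from 55.7% to 44.8% and 35.0%.

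**6. The *Recovery* default has the mirror effect.** With d comparator men scored *Recovery*, none in Dysport and 20% true recovery, rejection is again 1.7%, 3.3% and 5.8%. At 50% true recovery it is 1.2%, 1.8% and 2.7%.

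**The case against.** The strongest reply is that the literal reading is not the only one. Protocol 7.2 places the withdrawal visit at the time of discontinuing, so its CMAP need not follow the event. The rule's last clause ("in case of no available CMAP after this ICE") would then apply, giving *Recovery*. For a mistimed target visit the event sits at that visit, and a later low CMAP is reasonable evidence of non-recovery. This stands: for withdrawals the fault is an unresolved ambiguity, not a certain misclassification. It does not remove the problem, because the two readings give opposite scores and the SAP does not choose between them.

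A reader might infer that the rule favours Dysport. The documents do not support that. The wording is identical for all arms, and the direction depends on who withdraws.

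A reader might also infer that the rule cancels a recovery already reached, for example 86% at Week 20 followed by 82% at withdrawal. The carry-forward sentence answers this: that man is recovered from Week 20, and nothing says the imputation overrides the definition.

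Finally, the recovery tests are gated. Week 28 recovery is tested only after both primary and both Week 40 amplitude hypotheses are rejected, and Week 40 recovery only after both Week 28 recovery hypotheses are rejected. The rates above are therefore marginal test rates, not error rates of the planned procedure. This stands too.

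**Conclusion.** The point holds as a defect of specification. SAP 5.7.3.1 ties the imputing CMAP to the intercurrent event and sets no condition relative to Week 28 or Week 40. A withdrawn man's score is then either based on a value that cannot show it or left to the programmer's reading, and the sentence on ignoring post-deviation data conflicts with the rule for deviations.

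The size depends on unknown withdrawal. At 80% true recovery with Dysport-only withdrawals, two such men take the marginal rejection rate above 2.5%. With equal withdrawal the test becomes more conservative and a true difference is diluted. The documents do not show a built-in advantage for Dysport or an inflated family-wise error rate. The primary endpoint is not affected. The change should be made because it costs little and the endpoints are alpha-controlled.

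**What to change.** Before database lock, amend SAP 5.7.3.1 along these lines:

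- For Week X (28 or 40), the next available CMAP is the first one dated within or after the Week X window of ±2 weeks.
- An earlier CMAP, including one from the early-withdrawal visit, does not qualify. The rule for no available CMAP then applies.
- State whether the sentence that ignores post-deviation assessments covers the recovery endpoints, and how a man given the wrong intervention is scored.
- For clarity, repeat that a recovery reached before the event is kept.

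This sends early withdrawals to the *Recovery* default, which favours Dysport when comparator men withdraw. Add a sensitivity analysis that is worst case by arm: unobserved Dysport men scored *Recovery*, unobserved comparator men scored *No recovery*.

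The cost is a few sentences and one extra analysis, with no new data. The small downside is that a few early withdrawals move to the default score.
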